4.1.2. Baseline Definition

For all endpoints the baseline value will be the latest pre-dose assessment with a non-missing value, including those from unscheduled visits, unless otherwise stated. If time is

not collected, Day 1 assessments are assumed to be taken prior to first dose and used as baseline.

If baseline data is missing no derivation will be performed and baseline will be set to missing.

For PP-NRS and Item 3 baseline, the baseline score will be averaged from daily values from Day -7 to Day -1, if ≥ 4 (out of 7) days are not missing. If only ≤ 3 days (out of 7) are available, baseline is set to missing.

For skin punch biopsy, there is a Lesional Baseline and a Non-lesional Baseline.

4.2. Primary Endpoint Analyses

4.2.1. Definition of Percent change from baseline in the EASI

The primary endpoint is the Percent change from baseline in the EASI at Week 12 in Group 1, and the estimand is described in Section 1.1.

4.2.2. Main analytical approach

The analysis will be carried out for Group 1 only, using data up to Week 12.

The analysis will be based on the Safety analysis set. Participants will be analysed according to the treatment they received.

EASI scores collected after use of Rescue Therapy will be set to missing.

Missing observations will be assumed to be Missing at Random (MAR), i.e. assume that the missing part, given the history, will be like the data observed in the absence of Rescue Therapy.

Endpoint(s)				
 Percent Change from Baseline in the EASI at Week 12 (Group 1) (Hypothetical Strategy, robust MAP Prior) 				
Analysis Metho	d			
Bayesian repeat	ed measures model			
Model Specifica	ation			
Outcome	Percent change from baseline in the EASI			
Baseline EASI score (continuous)				
Treatment (categorical, reference: placebo)				
Predictors	 Visit (categorical, weeks 2, 4, 8, 12, reference: Week 12) 			
	Treatment*visit interaction (categorical)			
	Baseline EASI*visit interaction (continuous)			

	Baseline EASI score will be centered around its observed mean prior to inclusion in the model		
Prior distributions for parameters associated to the predictors	 Placebo at Week 12: robust MAP prior: mixture prior has 28.5% weight on a Normal (-31.56, SD=5.67), 21.5% weight on a Normal (-31.21, SD=11.00) and 50% weight on a Normal (-30, SD = 50) GSK1070806 at Week 12: vague prior Normal(-30, SD=50) All other parameters: vague priors Normal(0, SD = 106) 		
Prior distribution for residual covariance matrix	• Σ: unstructured residual covariance matrix of dimension 4×4 ~ Inverse Wishart (J, S), with J = number of visits (degree of freedom), S = identity matrix		
	If convergence issues occur, an alternative covariance matrix structure may be used, for example a compound symmetric structure, to help improve convergence.		

Model Checking & Diagnostics

See Section 4.1.1

Results Presentation

- Adjusted posterior median, and 95% Crl for each treatment by timepoint interaction (table).
- Posterior median treatment differences (GSK1070806 placebo) and associated 95% Crl for each timepoint (table and figure).
- Probabilities that the true treatment difference (GSK1070806 placebo) at each visit is < 0%, 15%, -25%, and -40% (table), e.g., Prob(GSK1070806 placebo < -15%)
- Outputs will include results for earlier timepoints in addition to the objective specified timepoint of Week 12.

For the PCFB in the EASI at Week 12 in the placebo arm, data from 16 previous trials in AtD were included to derive an informative prior using a meta-analytic predictive (MAP) method [Schmidli, 2014]. A vague mixture component was added to allow for prior-data conflicts.

Data were extracted from the following publications: [Beck, 2014], [Bissonnette, 2019], [Gooderham, 2019], [Guttman-Yassky, 2019], [Guttman-Yassky, 2020a], [Guttman-Yassky, 2020b], [Ruzicka, 2017], [Simpson, 2016], [Simpson, 2018], [Simpson, 2019], [Simpson, 2020], [Thaçi, 2016].

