6.3. Measures to Minimize Bias: Randomization and Blinding

Blinded study with unblinded site pharmacist who is dispensing intervention

All participants will be centrally randomized using an Interactive Voice/Web Response System (IVRS/IWRS): RAMOS-NG.

Before the study is initiated, the telephone number and call-in directions for the IVRS and/or the log in information and directions for the IWRS will be provided to each site.

Participants will be randomized in a 2:1 ratio (Group 1 Biologic Naïve versus placebo) or 5:1 ratio (Group 2 Dupi-IR) to receive study intervention.

Investigators will remain blind to each participant's assigned study intervention.

In order to maintain the blind, an otherwise uninvolved 3rd party will be responsible for the dispensing of study intervention and will endeavour to ensure that there are no differences in the preparation time following randomization.

Unblinded monitors, and in the event of a Quality Assurance audit, the auditor(s) will be permitted access to un-blinded study intervention records at the site(s) to verify that randomization/dispensing has been done accurately.

A participant may continue in the study if that participant's intervention assignment is unblinded.

GSK's Global Clinical Safety and Pharmacovigilance (GCSP) staff may unblind the intervention assignment for any participant with an SAE. If the SAE requires that an expedited regulatory report be sent to one or more regulatory agencies, a copy of the report, identifying the participant's intervention assignment, may be sent to investigators in accordance with local regulations and/or GSK policy.

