Rationale for estimand: The study is designed to evaluate the treatment effect attributable to GSK1070806. It is important that this effect is not confounded by the effect of other treatments. Therefore, for participants who use any Rescue Therapy, a hypothetical strategy will be used in order to estimate the treatment effect in the absence of use of Rescue Therapy.

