3. ANALYSIS SETS

For the purposes of analysis, the following analysis sets are defined:

Analysis Set	Definition / Criteria	Analyses Evaluated
Screened	All participants who signed the ICF and are screened for eligibility.	Study Population
Enrolled	All participants in the Screened analysis set who entered the study.	Study Population
Randomised	 All participants in the Enrolled analysis set who were randomly assigned to study intervention in the study. Participants will be analysed according to the intervention they were randomized to receive. 	Study Population
Safety	 All participants in the Randomized analysis set who received the study intervention. Participants will be analysed according to the intervention they actually received. 	EfficacySafetyBiomarkerPROs
Pharmacokinetic (PK)	 All participants in the Safety analysis set who had at least 1 non-missing PK assessment (Non-quantifiable [NQ] values will be considered as non-missing values). Participants will be analysed according to the intervention they actually received. 	• PK
COVID-19	All participants in Safety analysis set who had confirmed COVID-19 diagnosis.	Safety

The term "Analysis Set" will be referred to as "Population" in the displays.

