4.2.3. Sensitivity analyses

As a sensitivity analysis, a vague prior of Normal (-30, SD=50) will be applied instead of the robust MAP prior for placebo at Week 12.

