5. SAMPLE SIZE DETERMINATION

Approximately 64 patients may need to be screened to obtain 48 randomized participants (approximately 30 and 18 participants in Groups 1 and 2, respectively). Participants who have withdrawn from the study, may be replaced at the discretion of the sponsor.

The sample sizes for Groups 1 and 2 are selected to support preliminary assessment of the clinical effect, based on PCFB in the EASI for Groups 1 and 2.

Operating characteristics of some criteria of interest for the both groups of the study have been calculated and presented below.

Group 1:

Based on 30 participants (20 administered GSK1070806 and 10 administered placebo), the probability of different criteria of interest are given in the table below.

A Bayesian linear regression was used, assuming that the PCFB in the EASI follows a Normal distribution. The priors were as follows:

- Placebo arm: a robust meta-analytic predictive (MAP) prior was constructed based on placebo PCFB in the EASI reported in recent clinical trials in AtD. The resulting mixture prior has 28.5% weight on a Normal (-31.56, SD=5.67), 21.5% weight on a Normal (-31.21, SD=11.00) and 50% weight on a Normal (-30, SD = 50), with an effective sample size of 14 participants (expected local-information-ratio (ELIR) method (Neuenschwander, 2020)) assuming a between-participant SD = 50.
- GSK1070806 arm: a vague Normal prior was used, with mean = -30 and SD = 50, corresponding to an effective sample size (ELIR method) of 1 participant assuming a between-participant SD = 50.

Operating characteristics are provided below. A true PCFB in the EASI of -30% in the placebo arm was assumed, based on recent clinical trials in AtD. Various true PCFBs in the EASI for the GSK1070806 arm at Week 12 were assumed, giving various true treatment differences. A between-participant SD of 50% was assumed for both GSK1070806 and Placebo arms.

Criteria	True treatment difference			
	-40%	-25%	-15%	0%
Observing a >75% posterior probability that the true difference from placebo is <-15%	82.6%	43.9%	18.4%	2.5%
Observing a >75% posterior probability that the true difference from placebo is <-7.5%	92.8%	66.6%	37.7%	7.8%
Observing a >97.5% posterior probability that the true difference from placebo is < 0%	68.8%	30.3%	10.9%	1.0%

Group 2:

There are no planned statistical analyses comparing GSK1070806 *versus* placebo. The analysis will be conducted on PCFB in the EASI in the GSK1070806 arm.

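### Group 1 efficacy is compared by treatment received with no planned analysis by randomised arm; this matters only if a participant is given the wrong product

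*SAP*

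**What the plan says.** SAP 4.2.2 sets the rule for the primary endpoint: "The analysis will be based on the Safety analysis set. Participants will be analysed according to the treatment they received". Protocol 9.4.2 has the same rule, so the two documents agree. SAP 4.3.1.2 repeats it for the secondary efficacy endpoints, and SAP 4.7 applies the analysis of 4.2.2 at the interim.

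SAP 3 defines the Safety set as "All participants in the Randomized analysis set who received the study intervention", by actual intervention. It also defines a Randomised set, for which "Participants will be analysed according to the intervention they were randomized to receive", but assigns that set only to study-population displays.

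No reason is given for choosing treatment received for efficacy. The one sensitivity analysis for the primary endpoint concerns the placebo prior: "As a sensitivity analysis, a vague prior of Normal (-30, SD=50) will be applied instead of the robust MAP prior". The additional estimands in SAP 4.2.4 concern rescue therapy and COVID-19. SAP 4.3.1.3 plans no sensitivity analysis for secondary efficacy, and the supplementary analysis that can be read in SAP 4.3.1.4 concerns data after rescue. Parts of the SAP are redacted, so this describes the readable text.

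**The concern.** The primary objective compares active with placebo in Group 1, and the 2:1 randomisation is what makes the arms comparable. If arm membership can change according to what was infused, that comparability no longer holds for the participants who move.

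A wrong-product error is possible. Under Protocol 6.1, active is diluted at the site from vials and placebo is locally sourced saline. The SAP foresees a neighbouring error: SAP 4.1 has a rule for participants randomised in the wrong group.

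With 10 placebo participants planned, one participant carries weight. If an error happened to involve someone with an unusually good or poor course, treatment received would carry that person's prognosis into the other arm. Nothing planned would show how far the result depended on it.

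**Working it through.** **Inputs.** Group 1 has 20 active and 10 placebo participants (SAP 5). "A between-participant SD of 50% was assumed for both GSK1070806 and Placebo arms". The true placebo mean is taken as -30. The placebo prior at Week 12 is the mixture 28.5% N(-31.56, SD 5.67), 21.5% N(-31.21, SD 11.00) and 50% N(-30, SD 50). The active prior is N(-30, SD 50). The documents give no wrong-product rate, so the number of errors and the participant's prognosis below are assumptions.

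**Step 1: the plan's own figures.** Arm means were simulated with SD 50 taken as known, and the stated priors were updated (200,000 trials per scenario). At true differences -40/-25/-15/0:

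- Criterion 1 (over 75% probability of a difference below -15): 82.7/43.9/18.3/2.6%, stated 82.6/43.9/18.4/2.5%.
- Criterion 2 (over 75% probability, below -7.5): 92.8/66.6/37.5/7.8%, stated 92.8/66.6/37.7/7.8%.
- Criterion 3 (over 97.5% probability, below 0): 68.8/30.3/10.9/1.0%, as stated.

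The table assumes that everyone receives the product they were randomised to, so the choice of rule changes none of it.

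**Step 2: no wrong-product errors.** Both rules give 20 v 10 with the same people in each arm, so the results are identical.

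**Step 3: one error related to prognosis, no drug effect.** Assume that both randomised arms average -30 and that one placebo-randomised participant, at -80 (50 points better), was given active.

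- By randomised arm: -30 - (-30) = 0.
- By treatment received, active: (20 × -30 - 80)/21 = -32.38.
- By treatment received, placebo: (10 × -30 + 80)/9 = -24.44.
- Raw difference: -32.38 + 24.44 = -7.94, which equals -(50/21 + 50/9).
- For a participant 25 points better: -(25/21 + 25/9) = -3.97.

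**Step 4: the same case under the stated priors.** SD 50 is taken as known, which simplifies the repeated measures model.

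- Active: the posterior weight on the data is 21/22, so the mean moves by 2.38 × 21/22 = 2.27 points, from -30.0 to -32.3.
- Placebo, mixture prior, n = 9: the posterior mean moves from -30.9 to -28.7, about 2.1 points instead of the raw 50/9 = 5.6.
- Difference: about 2.27 + 2.13 = 4.4 points in favour of active (about 2.2 for a participant 25 points better).
- With the vague placebo prior of SAP 4.2.3 the weight on the data is 9/10, so the shift is 2.27 + 5.56 × 9/10 = 7.3 points.

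For scale, the raw standard error at 20 v 10 is 50 × √(1/20 + 1/10) = 19.4 points.

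**Step 5: one error unrelated to prognosis, true difference -40** (active -70, placebo -30).

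- Placebo participant given active, by randomised arm: placebo mean (9 × -30 - 70)/10 = -34, difference -36. Criterion 1 is met with probability about 78.0% instead of 82.6%.
- Active participant given placebo, by randomised arm: active mean (19 × -70 - 30)/20 = -68, difference -38. Criterion 1 is met with probability about 78.9%.
- By treatment received: the expected difference stays -40 and the probability stays at 82-83% in both cases.
- With a true difference of 0, both rules give about 2.5% for criterion 1 and 1.0% for criterion 3.

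**The case against.** The best defence is that the rule rarely has any effect and is arguable when it does.

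- **Little room for error.** There is one infusion on Day 1, so later switching and non-adherence cannot arise. Protocol 6.4 has a second staff member confirm dose and identity at dosing. Protocol 6.3 has an uninvolved third party dispense, keeps investigators blind and lets unblinded monitors verify dispensing. Bias also needs an error related to prognosis, and the documents suggest no mechanism for one. All of this stands, and it is why the point is minor.
- **A real advantage.** SAP 1.1 says: "The study is designed to evaluate the treatment effect attributable to GSK1070806". If errors are unrelated to prognosis, treatment received avoids the dilution in Step 5. In a Phase Ib estimation study with no formal hypothesis this is a coherent choice. That also stands. However, with 30 participants nobody can verify that an error was unrelated to prognosis, and analysis by randomised arm does not need that assumption.
- **The priors dampen the effect.** This is correct for the main analysis (4.4 against 7.9 points), but much less so for the vague-prior analysis (7.3).

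A reader might infer that the plan abandons randomisation altogether, or that treatment received brings no benefit. The documents support neither: without a wrong-product error nothing changes, and Step 5 shows a benefit in one plausible case. Nor should the 5.6-point move in the raw placebo mean be read as the effect on the primary result, which is a difference estimated under an informative placebo prior.

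**Conclusion.** The point holds as a minor one. Protocol 9.4.2 and SAP 4.2.2 and 4.3.1.2 put the randomised Group 1 efficacy comparison on an as-received basis, and nothing planned shows the result by randomised arm.

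The exposure is conditional on a wrong-product error related to prognosis. For one such participant, 25 to 50 points better than the arm mean, the shift is about 4.0 to 7.9 points on the raw difference and about 2.2 to 4.4 points under the stated priors. It rests on the assumed error, the assumed prognosis and SD 50 treated as known. With no errors the result is unchanged, and none of the plan's stated operating characteristics is called into question.

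Separately, the Safety set leaves out anyone randomised but not dosed. That follows from the choice of set, not from the as-received rule. Losing one participant per arm would lower criterion 1 at -40 from 82.6% to about 81.2%.

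**What to change.** - Analyse the Group 1 primary and secondary efficacy endpoints in randomised and dosed participants, by randomised arm.
- Keep the as-received analysis as a sensitivity analysis.
- Keep treatment received for safety, PK and immunogenicity.
- Report the numbers mis-dosed and undosed, by randomised arm.

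**Cost.** The text change is short but touches several places, because the Safety set definition itself carries the as-received rule. An efficacy exception is needed in Protocol 9.4.2 and 9.4.3.2 and in SAP 3, 4.1, 4.2.2 and 4.3.1.2. The interim analysis follows, since SAP 4.7 points to 4.2.2. A protocol amendment needs ethics approval before it takes effect (Protocol 10.1.1). If one is not wanted for this alone, adding the as-randomised analysis to SAP 4.2.3 and 4.3.1.3 as a sensitivity analysis before unblinding would cover most of the concern. No extra data are needed.

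The statistical price is dilution if an error unrelated to prognosis occurs, for example -40 to -36 for one placebo participant given active. The as-received sensitivity analysis would show it.

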9.4.2. Primary Endpoint(s)

The primary endpoint is the PCFB in the EASI at Wk 12 in Group 1. The population-level summary is the treatment difference (GSK1070806 – placebo) in PCFB in the EASI scores at Wk 12.

The analysis will be based on the Safety analysis set. Participants will be analysed according to the treatment they received.

A Bayesian repeated measures model will be used, including study treatment, visit, study treatment-by-visit interactions, baseline EASI value, baseline-by-visit interactions and subject-level repeated measures.

Priors defined in Section 9.2 will be used for the analyses. For the MAP prior, details of the included studies will be documented in the SAP. An inverse Wishart prior will be used for the within-subject unstructured covariance. Other options may be investigated to determine an appropriate covariance structure in case of issues.

A Bayesian repeated measures analysis will be conducted under the missing-at-random assumption.

Further details on any sensitivity estimators used to assess the primary objective will be provided in the SAP.

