The PCFB in the EASI in Group 2 in the GSK1070806 arm will be analysed using a simplified version of the approach used for the primary endpoint (Section 4.2.2) with only one treatment arm. EASI scores will be set to missing after Rescue Therapy. Missing values are assumed to be Missing at Random (MAR). Vague priors of Normal(0, SD=10⁶) will be used for the parameters associated to the predictors.

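### The only fallback covariance that the SAP names, compound symmetry, pools variance over Weeks 2 to 12 and misstates Week 12 uncertainty unless the Week 12 variance equals the visit average

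*SAP*

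**What the plan says.** SAP Section 4.2.2 fits a Bayesian repeated measures model to percent change from baseline in EASI at Weeks 2, 4, 8 and 12. It includes treatment-by-visit and baseline-by-visit terms and an "unstructured residual covariance matrix of dimension 4×4" with an inverse Wishart prior. It then adds that, should the model have trouble converging, "an alternative covariance matrix structure may be used, for example a compound symmetric structure". Protocol Section 9.4.2 is more open and names no structure: "Other options may be investigated to determine an appropriate covariance structure in case of issues".

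The approach is reused elsewhere:
- Change from baseline in Group 1 follows Section 4.2.2 with vague priors (SAP 4.3.1.2).
- Group 2 uses a "simplified version of the approach used for the primary endpoint" with one arm and vague priors (SAP 4.3.1.2).
- The interim predictions come from the Section 4.2.2 analysis (SAP 4.7), with about half of Group 1 through Week 12 (Protocol 9.5.2).

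The only between-participant SD in either document is the planning value in SAP Section 5: "A between-participant SD of 50% was assumed for both GSK1070806 and Placebo arms".

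**The concern.** Compound symmetry without further qualification means one variance for all visits and one correlation. For a score measured on its own scale that can be a fair simplification. For change from baseline it is less natural: every participant has zero change at baseline, so spread starts at zero, and Week 2 is the modelled visit nearest that point. If spread is still growing between Week 2 and Week 12, the average variance over visits is smaller than the Week 12 variance, and the inference at the primary time point borrows precision that it does not have.

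The error would be hard to see. Treatment and baseline both interact with visit, so with complete data and flat priors the Week 12 estimate is the same under either structure, and only its stated uncertainty moves. The planned sensitivity analysis (SAP 4.2.3) changes only the placebo prior. In Group 2 and for change from baseline no MAP prior cushions the effect. At the interim, 10 covariance parameters would be estimated from about 15 participants, and the result can stop the study.

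**Working it through.** **Inputs from the documents (SAP 4.2.2 and 5).** Group 1 has 20 active and 10 placebo participants, with SD 50 in both arms and a true placebo mean of -30. The placebo prior is 0.285 N(-31.56, SD 5.67) + 0.215 N(-31.21, SD 11.00) + 0.50 N(-30, SD 50). The active prior is N(-30, SD 50).

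**Assumed inputs.** The documents give no SDs for Weeks 2, 4 and 8, so a range is used, with Week 12 fixed at 50. Data are complete.

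**Step 1: reproduce the plan's figures.** With normal data, known SD 50 and the priors above, 200,000 simulated trials reproduce all 12 Group 1 operating characteristics within 0.2 points. Under no effect the three criteria (difference < -15, < -7.5, < 0) give 2.5%, 7.8% and 1.1%, against the stated 2.5%, 7.8% and 1.0%.

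**Step 2: Week 12 SD under compound symmetry.** With complete data and every predictor crossed with visit, the common variance is the mean of the four visit variances:

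SD(pooled) = sqrt[(SD2² + SD4² + SD8² + SD12²)/4]

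- 40/45/48/50: sqrt(8429/4) = sqrt(2107.25) = 45.9
- 30/38/46/50: sqrt(6960/4) = sqrt(1740) = 41.7
- 25/35/44/50: sqrt(6286/4) = sqrt(1571.5) = 39.6
- 60/58/54/50: sqrt(12380/4) = sqrt(3095) = 55.6

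**Step 3: consequences at Week 12.** The true SD is 50 and the analysis uses the pooled SD. Without an informative prior, coverage is 2Φ(1.96 × SD(pooled)/50) - 1; for example, 1.96 × 41.7/50 = 1.635, giving 89.8%. The columns under the MAP prior come from simulation with the Step 1 model, at a true difference of 0.

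| SD at Weeks 2/4/8/12 | Pooled SD | Coverage, no informative prior | Coverage, MAP prior | >97.5% that difference < 0 | >75% that difference < -7.5 |
|---|---|---|---|---|---|
| 50/50/50/50 | 50.0 | 95.0% | 97.6% | about 1.0% | 7.7% |
| 40/45/48/50 | 45.9 | 92.8% | 96.1% | 1.8% | 9.1% |
| 30/38/46/50 | 41.7 | 89.8% | 93.7% | 2.9% | 10.7% |
| 25/35/44/50 | 39.6 | 88.0% | 92.2% | 3.6% | 11.6% |
| 60/58/54/50 | 55.6 | 97.1% | 98.9% | 0.5% | 6.2% |

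**Step 4: cross-check with the SD estimated.** In 30,000 simulated four-visit trials (assumed correlation 0.6), the residual SD was estimated instead of fixed. Mean 95% interval width with the MAP prior changes as follows from unstructured to compound symmetry: 62.4 to 58.5 points for 40/45/48/50, 62.5 to 68.4 for 60/58/54/50, and 62.4 to 62.7 for equal SDs. Direction and size agree with Step 3.

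**Step 5: Group 2.** With 15 active participants the standard error is 50/sqrt(15) = 12.9. For 30/38/46/50 compound symmetry would report 41.7/sqrt(15) = 10.8. The Group 2 criteria in SAP Section 5 use a 50% posterior threshold, so with complete data they are essentially unaffected; the interval is affected.

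**The case against.** The strongest reply is that this is a contingency. The planned matrix is unstructured, the alternative applies only after convergence trouble, compound symmetry is an example, and the protocol wording already allows a heterogeneous structure. That stands: nothing is wrong unless the fallback is used.

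The trigger may also be remote. A trial run of the unstructured sampler on simulated complete data, with the vague placebo prior, gave a worst Gelman-Rubin value of 1.001 at both 20+10 and 10+5 participants, against the SAP cut-off of 1.1. It did not include the mixture prior or missing data. A reader might infer that the small sample will force compound symmetry; the documents do not show that.

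A reader might also infer that the Week 12 interval is bound to be too narrow. Zero change at baseline fixes the spread at a time that is not modelled; it does not prove that variance still rises from Week 2 to Week 12. Percent change cannot fall below -100%, and scores after rescue are set to missing, both of which can trim late spread. The last row of the table shows the reversal.

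Nor is every posterior probability inflated. A smaller SD lowers the probability of any threshold beyond the estimate. With observed means of -30 on placebo and -35 on active, P(difference < -15) falls from 0.215 at SD 50 to 0.182 at SD 41.7.

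Finally, the coverage figures without an informative prior do not describe the primary analysis. With the MAP prior the mildest rising pattern still covers 96.1%. The tabulated criteria are described as criteria of interest, no formal hypothesis is tested, and the interim decision criteria sit in a charter outside these documents.

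**Conclusion.** The point holds as a conditional one. If the unstructured model fails to converge and the named example is adopted, Week 12 uncertainty is misstated whenever the Week 12 variance differs from the visit average. Growth in spread is the more plausible direction for a change score, but neither document supplies the SDs to confirm it.

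Under the three rising patterns the pooled SD is 8% to 21% below 50, with the losses of coverage shown in the table. With the MAP prior these are moderate, and the mildest pattern stays above the nominal 95%. With equal SDs there is no effect.

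The figures rest on assumed SD patterns, complete data and a normal outcome. With missing Week 12 values the choice of structure could also move the point estimate; that was not computed. The possible reversal does not weaken the case for a change, because a structure with visit-specific variances avoids the error in both directions.

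**What to change.** Replace the compound symmetry example in SAP Section 4.2.2 with an ordered rule:

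1. If the diagnostics in Section 4.1.1 are not met, first run longer or thinned chains, which that section already allows.
2. If a simpler structure is still needed, use one that keeps a separate variance for each visit, for example heterogeneous compound symmetry or heterogeneous AR(1), with the priors for the SDs and the correlation written down.
3. Do not use homogeneous compound symmetry for Week 12 inference.

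State that the same rule applies to change from baseline, Group 2 and the interim.

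A regression on Week 12 alone is not a good preferred fallback, although the sample size work used a simple linear regression. It discards the earlier visits that support the missing-at-random assumption once values after rescue are removed.

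The cost is a short SAP edit. Either heterogeneous structure has 5 covariance parameters (four variances and one correlation), against 2 for compound symmetry and 10 for unstructured. That is three more variances than compound symmetry, plus priors that the SAP does not yet give, but still half the unstructured count.
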